### **1.3 Side effects associated with breast cancer adjuvant endocrine therapy**

Across all adjuvant endocrine trials, regardless of the treatment received, vasomotor symptoms such as hot flushes are the most common adverse events. Other frequently reported side effects, such as vaginal discharge, vaginal dryness, dyspareunia and arthralgia, vary in prevalence between tamoxifen and AIs (5). Data from a study specifically addressing menopausal

symptoms after breast cancer showed that hot flushes (41%), night sweats (36%), loss of interest in sex (30%), difficulty sleeping (25%), fatigue (22%) and extreme vaginal dryness (19%) were the most common adverse effects, being the urogenital symptoms such as the vaginal dryness and sexual dysfunction due to vaginal atrophy of particular high prevalence with the treatment with AIs (8).

#### **1.4 Management of sexual adverse effects derived from the treatment of breast cancer patients**

Taking into consideration that many women diagnosed with breast cancer today will be long-term survivors of their disease, the long-term impact of therapy on their well-being and specifically on their sexual adverse effects has become a growing topic for research (9).

In order to overcome symptoms of estrogen deprivation, vaginal moisturizers or, sometimes, low dose topical estrogens are used in daily clinical practice, despite the inexistence of adequate clinical trials that support their use. Non-hormone vaginal moisturizers relieve urogenital symptoms, however their efficacy is significantly lower compared to vaginal estrogens (10). In contrast to oral hormone therapy, some consider that local application of estrogens seems to be safe in postmenopausal breast cancer patients (11). However, the report of a small prospective observation (12) advised caution with the use of vaginal estradiol in breast cancer patients receiving aromatase inhibitors, as an increase of serum estradiol levels was found that potentially could counteract endocrine breast cancer treatment (13).

A study using lower doses of estradiol presented in the 2013 ASCO Annual Meeting showed no changes in FSH while sporadic elevations of estradiol were seen in 5 out of 26 studied patients. The significance of this is difficult to judge as the full results have not been published yet (14).

According to the publication “*Practical guidelines for managing menopausal symptoms after breast cancer*”, the use of vaginal estradiol in patients treated with aromatase inhibitors was discouraged, but there was recommended the application of vaginal estriol, a much less potent estrogen than estradiol, in case estrogen therapy were deemed necessary (15).

However, safety data of vaginal estriol in breast cancer patients receiving aromatase inhibitors are scarce. Pfeiler et al prospectively investigated the safety of vaginal estriol in 10 postmenopausal breast cancer patients receiving AIs by measuring serum hormone levels before and 2 weeks after daily application of currently marketed dose of 0.5 mg vaginal estriol (Ovestin). In this study no elevation of serum estriol or estradiol could be detected, but a significant decline in serum follicle stimulating hormone and luteinizing hormone was observed (fell from a mean value of 75.7 to 66.0 mIU/ml after two weeks of daily vaginal treatment with 0.5 g of estriol). The conclusion of this study was that vaginal estriol did not lead to a long term elevation of serum estrogen levels (although the analytical methodology employed lacked sufficient sensitivity and the number of patients was very low); nevertheless the significant decline in gonadotropins indicated a systemic effect, which had to be kept in mind when offering vaginal estriol at the dose of 0.5 mg per application to breast cancer patients on aromatase inhibitors (16).

### **1.5 Role of 0.005% estriol vaginal gel (Blissel®) in the Treatment of vaginal atrophy**

0.005% Estriol vaginal gel is a new formulation for the local treatment of postmenopausal vaginal atrophy, which delivers an ultra-low dose of estriol per application (50 µg), ten times lower than the current dose of this hormone currently used in clinical practice. It is marketed under the trade names of Blissel® or Gelistrol® in several European countries since 2012.

This new formulation has proven to be efficacious in relieving vaginal dryness as well as improving the most typical signs of the atrophy in a cohort of postmenopausal women (17). A pharmacokinetic study compared the systemic absorption of estriol of the new formulation vs the reference product (Ovestinon vaginal cream 0.1%, 0.5 mg of estriol per application). After three weeks daily treatment, it was shown that Blissel produced negligible plasma estriol levels and significantly lower than those produced by Ovestinon ( $p < 0.0001$ ). In addition, 0.005% estriol formulation did not change serum FSH or LH while a significant decline of serum FSH was observed in women that received Ovestinon ( $p = 0.0425$ ) (18,19).

These data suggested that Blissel could potentially be safe in postmenopausal patients treated with aromatase inhibitors; however these results were obtained in a cohort of healthy postmenopausal women.

### **1.6 Study Rationale**

In order to explore the safety of 0.005% estriol vaginal gel in the oncological context, a new safety study is proposed with the hypothesis that 0.005% estriol vaginal gel is a safe therapeutic option to treat the vaginal atrophy caused by AIs, without a significant decline in gonadotropin or increase in systemic estrogen levels in hormone receptor-positive postmenopausal women with early stage breast cancer in treatment with non-steroidal aromatase inhibitors (NSAIs) in the adjuvant setting.

---

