The differentiation between active and placebo in the subjective parameters of efficacy (secondary) would be possible at the expense of a sample size noticeably superior. Since the evaluation of effectiveness is not primary but secondary in this study, it is not justified in this study to increase the sample for this reason.

In accordance with the above, the study would include 55 women (44 will receive vaginal estriol gel and 11 with the placebo moisturizing gel). Taking into account 10% of dropouts, the sample to be considered is of 60 women (48 vaginal estriol gel and 12 placebo moisturizing gel). This is an unbalanced study but with an active: placebo ratio of 4:1, which will support an adequate patient randomization (blocks of 5).

10 additional women will be recruited in a first safety phase of the study (8 with vaginal estriol gel and 2 placebo moisturizing gel). It is expected that none of them will present with significant changes in FSH from postmenopausal to premenopausal levels.

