### 3.1.1 Early Safety Review

There will be an initial safety phase of the study, in which 10 patients will be included (also randomized 4:1) to obtain some preliminary safety data and FSH values prior to the recruitment of the rest of the group under study.

These women will receive the study treatment over 3 weeks (8 will receive estriol vaginal gel and 2 placebo moisturizing gel). FSH levels in serum will be analysed at screening, baseline and at week 3 (day 22 +/- 3 days). An independent data monitoring committee (IDMC) will review the results (together with safety data) which will advise the chief investigators about a go /no-go decision with the other 60 patients to complete the study. The study will continue if no significant changes in FSH levels from postmenopausal to premenopausal levels are observed.

These 10 patients will be recruited in two sites in Spain, 5 patients in each one. These patients will have estrogens, and FSH and LH determined at screening, baseline and at week 3.

**Figura 2:** Study Design of the Initial Safety Phase

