## 8. Sample Size and Statistical Methods

### 8.1 Determination of Sample Size

This is an exploratory study and there are scarce data to allow a precise sample size calculation. The most relevant data come from Pfeiler(16) who reported that the levels of FSH in patients treated with aromatase inhibitors fell from a mean value of 75.7 to 66.0 mIU/ml after two weeks of daily vaginal treatment with 0,5 g of estriol. Although no figures are reported of the variability of those measurements, an estimation of the standard deviation can be made applying the standard rule of  $[sd = \text{range}/4]$ . The reported range of FSH values in that report is 45.6 – 134.6, thus a reasonable approximation to the sd is  $89/4 = 22.3$ . Under these assumptions, it can be calculated that a sample size of 44 would provide 80% power to detect with an  $\alpha=0.05$  a decrease of FSH levels from 75.7 to 66.0 mIU/ml assuming a standard deviation of 22.3.

The hormone levels in women treated with IA who are not receiving estrogen therapy are likely to suffer physiological temporal oscillations. These variations could make difficult the interpretation of any eventual modification of hormone levels observed in the estriol treated women. In the absence of data of naturally occurring variations in hormone levels of women treated with IA that allow us to interpret the results of hormone determinations under study, it is considered appropriate to include a placebo group to provide reference data. In this case, the placebo is a vaginal moisturizing gel.

It is estimated that a group of 11 women will allow the assessment of physiological fluctuations in hormone levels. Additionally, this sample size for the placebo group will provide 80% power and  $\alpha=0.05$  to differentiate between active and placebo (ratio 4:1) on the change in the vaginal maturation value, which is a secondary variable of the study that provides objective information about the effectiveness of treatment on vaginal atrophy (calculation based on the parameter data from the pivotal Blissel study and considering only the subgroup of women who had severe vaginal dryness: change VM active group 24.9 vs 0.6 points in placebo group, SD = 24.2).

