### **8.2.3. Patient Characteristics**

Patient characteristics could include a summary of the following:

- patients demographics
- time of menopause
- baseline disease characteristics
- preexisting conditions/secondary conditions
- prior therapy

Other patient characteristics will be summarized as deemed appropriate.

The categorical variables will be summarized by contingency tables. The continuous variables will be described by the number of patients with valid values (n), mean, standard deviation, median and range in both arms.

The significance level of all statistical tests is established at 0.05.

The effect of the treatment on continuous variables will be assessed by paired-t analysis (or Mann-Whitney-Wilcoxon in case of lack of normality). Categorical variables will be analyzed by chi-cuadrado or Fisher's exact test.

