### **8.2.7. Efficacy**

The efficacy analysis will be evaluated in the ITT population.

The primary endpoint, the variation of FSH between week12 and baseline and comparing by arm will be analyzed using a non-parametric test (Mann-Whitney-Wilcoxon test).

An ANCOVA analysis will be used to corroborate the results obtained for the primary endpoint. The ANCOVA analysis will compare the variation of FSH 12 weeks adjusted by FSH basal between the two arms. This analysis will be performed if the relation between FSH 12 and FSH basal is lineal.

The variations in the intensities for each one of the symptoms and signs of the vaginal atrophy, after 3 and 12 weeks, in each treatment arm, will be compared using the non-parametric test Mann-Whitney-Wilcoxon.

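### The 80% power stated for FSH belongs to a within-arm test, not to the between-arm primary test, so a non-significant week-12 result cannot by itself support the hypothesis of no significant decline

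*Protocol*

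**What the plan says.** The hypothesis in section 1.6, repeated in the protocol summary, describes the product as "a safe therapeutic option to treat the vaginal atrophy caused by AIs, without a significant decline in gonadotropin or increase in systemic estrogen levels".

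Section 8.2.7 assigns the primary endpoint to a comparison between arms: "the variation of FSH between week12 and baseline and comparing by arm will be analyzed using a non-parametric test (Mann-Whitney-Wilcoxon test". A baseline-adjusted ANCOVA between arms is to corroborate it. Section 8.2.3 adds "The significance level of all statistical tests is established at 0.05".

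Section 8.1 bases the sample size on a fall in mean FSH from 75.7 to 66.0 mIU/ml with an SD of 22.3, and says that "a sample size of 44 would provide 80% power to detect" this. The placebo arm has a different basis. Because hormone levels fluctuate physiologically, "it is considered appropriate to include a placebo group to provide reference data", and 11 women are said to be enough for that and for 80% power on the vaginal maturation value. No FSH power is claimed for the comparison with placebo.

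Section 8.2.3, under patient characteristics, also says in general terms "The effect of the treatment on continuous variables will be assessed by paired-t analysis". Section 8.2.6 plans to study hormone change in each woman and to use the screening and baseline FSH values to describe intra-individual variation.

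The only decision rule on FSH concerns the 10-patient safety phase: "The study will continue if no significant changes in FSH levels from postmenopausal to premenopausal levels are observed". Those patients are left out of the final analysis (section 8.2.10).

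**The concern.** Three parts of the plan point in different directions. The hypothesis is the absence of a decline. The primary test can reject equality of the arms, but failing to reject does not show that FSH did not fall. The stated power belongs to a third question: whether FSH changes within the estriol arm alone.

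A reader who meets 80% power in section 8.1 and a non-significant p-value in the report would take the second as fairly strong evidence against a fall of the planning size. For the test in section 8.2.7 that inference fails unless the SD of change is near 10. Section 1.4 describes the decline in the planning study as a sign of systemic effect, and these are women on aromatase inhibitors for hormone-receptor-positive breast cancer. The trial could miss a fall of that size and still be reported as showing no significant decline. Estrogens are measured too, so FSH is not the only safety evidence, but it is the primary endpoint.

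**Working it through.** **Inputs.** From section 8.1: difference 75.7 − 66.0 = 9.7 mIU/ml; SD = (134.6 − 45.6)/4 = 22.25, which the protocol rounds to 22.3; alpha 0.05; 44 and 11 evaluable women. Two-sidedness is stated only for the secondary analyses (section 8.2.7.2), so it is assumed for the primary test.

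**Step 1: reproduce n = 44.** A two-sided one-sample (paired) t-test with difference 9.7 and SD 22.3 has power 80.5% at n = 44 and 79.6% at n = 43. So 44 is the smallest n that reaches 80%. One-sided versions give 33 to 35. A two-sample normal-approximation calculation gives 83 per arm at 1:1, or 208 plus 52 at 4:1. Only the within-arm version returns 44.

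**Step 2: same inputs, planned primary test.** Standard error = 22.3 × √(1/44 + 1/11) = 22.3 × 0.337 = 7.52. Power for 9.7 is 25.2% (normal approximation), 24.5% (noncentral t) and about 23% (simulated Mann-Whitney, normal data). A one-sided test would have about 36%. Reaching 80% at 4:1 with SD 22.3 would take 212 plus 53 women by t-test.

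**Step 3: what SD of change is plausible?** The 22.3 comes from a range of FSH levels, not of changes. If it is the SD at each time point, SD of change = 22.3 × √(2(1 − r)), where r is the assumed correlation between baseline and week 12. Then r = 0.90, 0.81 and 0.50 give about 10, 13.6 and 22.3.

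The protocol offers one indirect clue. The planning study found a significant 9.7 fall in 10 patients. If that came from a two-sided paired t-test at 0.05 (an assumption), the SD of change there was at most 9.7 × √10 / 2.262 = 13.6. That study lasted 2 weeks, so a larger SD at week 12 is possible.

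**Step 4: operating characteristics at 44 versus 11.** Mann-Whitney with exact critical value and Hodges-Lehmann interval, 40,000 simulated normal trials per case:

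| Assumed SD of change | t-test power for 9.7 | Mann-Whitney non-significant, true fall 9.7 | Mean half-width of 95% CI, between arms | Half-width, estriol arm alone (t) | CI excludes −9.7, no true effect |
|---|---|---|---|---|---|
| 10 | 81% | 22% | 7.0 | 3.0 | 78% |
| 13.6 | 55% | 48% | 9.5 | 4.1 | 51% |
| 22.3 | 24% | 77% | 15.6 | 6.8 | 23% |

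With a true fall of 9.7, the interval lies wholly above −9.7 in only about 2.4% of trials at every SD. The interval therefore seldom gives false reassurance at this reference point, whereas a non-significant p-value often would.

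**Step 5: the reading rule needs a condition.** Calling every interval that contains −9.7 inconclusive would be wrong. With a true 9.7 fall, a significant decline whose interval also contains −9.7 occurs in about 75%, 50% and 20% of trials at SDs 10, 13.6 and 22.3. The inconclusive label must apply to non-significant results only.

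**The case against.** Several points on the other side have weight.

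- **The study is exploratory and its objective is only to evaluate FSH levels.** True, and no sentence says that non-significance will prove safety. A reader might infer that the protocol plans to claim safety from a p-value; the text does not go that far. It does state a hypothesis, a power, an alpha and a primary test, and these do not match.
- **The SAP may give intervals and reading rules.** It may, and the protocol summary already promises 95% intervals for estimates of interest where possible. But the power statement and the primary test are both fixed in the protocol.
- **The within-arm analysis is in the plan.** Sections 8.2.3 and 8.2.6 support this, and it is what 44 was sized for. Nor is it wholly uncontrolled: every woman has two pre-treatment FSH values. Screening falls within 14 days of registration, so these describe short-term variation only and control for 12 weeks of fluctuation in part. Section 8.2.7 still makes the between-arm test primary.
- **Significant may mean a shift out of the postmenopausal range.** The safety-phase text uses the word so, for example "It is expected that none of them will present with significant changes in FSH from postmenopausal to premenopausal levels". Inclusion criterion 4 uses FSH above 40 mIU/ml on one route to postmenopausal status, but nothing links that value to the safety-phase rule or to week 12. Reading section 1.6 as statistical significance is one interpretation; on the other reading, the difference test addresses the hypothesis even less directly.
- **Miss rates near 77% rest on SD 22.3.** Fair. That is the SD that the protocol's own calculation treats as the SD of change, but its source study suggests a smaller one. The 22% to 48% range is better supported.

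**Conclusion.** The point holds as a mismatch between hypothesis, sample size and primary test. The 80% power applies to the within-estriol-arm change. For the test in section 8.2.7, power against the same fall is about 23% to 25% at the protocol's SD, and the miss rate is still 22% to 48% at SDs of 10 to 13.6. A non-significant p-value therefore cannot by itself support the hypothesis.

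The figures assume normally distributed changes, equal SD in both arms, a two-sided 0.05 test and 44 plus 11 evaluable women. The SD of change is an assumption throughout, and the 13.6 ceiling also assumes how the planning study was tested.

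Two stronger readings are not supported. The design has not failed: if the SD of change is about 10, the between-arm comparison has close to 80% power, and the placebo group was openly sized for other purposes. Nor is 9.7 mIU/ml a safety margin: it is the planning effect, and the protocol gives no FSH limit for week 12.

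**What to change.** 1. In section 8.1, state that the 80% power refers to the FSH change within the estriol arm and not to the between-arm primary test. Give the between-arm power over a range of assumed SDs of change (by t-test about 81%, 55% and 24% at 10, 13.6 and 22.3).
2. In section 8.2.7, keep the Mann-Whitney test as primary. Report with it the Hodges-Lehmann estriol-minus-placebo shift in week-12 FSH change and its two-sided 95% confidence interval. Add the ANCOVA estimate with its interval as corroboration. Give the within-arm change with its interval as supportive, read against the screening-to-baseline variation.
3. Add to section 8.2.7: *A confidence interval wholly below zero is reported as a decline in FSH, whether or not it includes −9.7 mIU/ml. A non-significant result will not be read as absence of a systemic effect; if it is non-significant and the interval includes a fall of 9.7 mIU/ml, the result is inconclusive. The 9.7 is the planning effect of section 8.1, a reference point and not a safety margin; excluding it does not by itself establish safety.*

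The cost is a sentence or two in 8.1 and a short paragraph in 8.2.7, possibly as a protocol amendment given section 8.2.1. The real price is that the FSH result may have to be reported as inconclusive: even with no true effect, the interval excludes −9.7 in only about 78%, 51% and 23% of trials at SDs 10, 13.6 and 22.3. The wording does not raise power; it stops low power being read as safety.

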## 2. Objectives

### 2.1 Primary Objective

The primary objective is to evaluate the levels of FSH after treatment with 0.005% estriol vaginal gel in hormone receptor-positive postmenopausal women with early stage breast cancer in treatment with NSAIs in the adjuvant setting and symptoms of vaginal atrophy.

### 2.2 Primary End-point

Variation in serum levels of FSH from baseline to 12 weeks of treatment.

### 2.3 Secondary Objectives

- To evaluate the levels of estriol, estradiol, estrone, FSH and LH after treatment with 0.005% estriol vaginal gel in hormone receptor-positive postmenopausal women with early stage breast cancer in treatment with NSAIs in the adjuvant setting and symptoms of vaginal atrophy.
- To assess the safety and tolerability of 0.005% estriol vaginal gel in hormone receptor-positive postmenopausal women with early stage breast cancer in treatment with NSAIs in the adjuvant setting and symptoms of vaginal atrophy.
- To assess the efficacy of 0.005% estriol vaginal gel in the treatment of symptoms and signs of vaginal atrophy in hormone receptor-positive postmenopausal women with early stage breast cancer in treatment with NSAIs and symptoms of vaginal atrophy.
- To measure the impact of treatment with 0.005% estriol vaginal gel in sexual function of hormone receptor-positive postmenopausal women with early stage breast cancer in treatment with NSAIs and symptoms of vaginal atrophy.

### 2.4 Secondary End-points

- Variation in serum levels of FSH at different time points compared to baseline (weeks 1, 3 and 8).
- Variation in serum levels of LH and plasma levels of estriol, estradiol and estrone, at different time points compared to baseline (weeks 1, 3, 8 and 12).
- AEs according to the Medical Dictionary for Regulatory Activities (MedDRA).
- Changes in vaginal dryness and other symptoms and signs of vaginal atrophy; change in vaginal maturation value and change in vaginal pH at week 3 and week 12 vs baseline.
- Changes in sexual function measured by the Female Sexual Function Index (FSFI) scale at week 3 and week 12 vs baseline.

### 3. Investigational Plan

#### 3.1 Study Design

This is a phase II, prospective, randomized, double-blind, placebo-controlled, international (Spain and Sweden) and multicentre study.

Sixty patients will be randomized (stratified by site) to receive 0.005% estriol vaginal gel (arm A) and placebo moisturizing gel (arm B) in a 4:1 proportion, so 48 patients will enter in arm A and 12 in arm B. Patients will undergo gynaecological tests, plasma and serum extraction for hormone determinations, adverse events collection and will answer a questionnaire according to what is outlined in Figure 1.

A) Patients randomized to Arm A (experimental arm) will receive:

Investigational drug product: 0.005% estriol vaginal gel (Blissel®)

Route: Vaginal. Administration by an applicator inserted deep inside the vagina

Dose: 1 g of gel, containing 50 µg of estriol

Dosage schedule: Weeks 1-3: single daily application  
Weeks 4-12: twice weekly administration.

[figure not shown]
Women will be instructed to administer the gel at bedtime.

B) Patients randomized to Arm B (control arm) will receive:

Placebo moisturizing gel (vehicle of Blissel®).

Same route and dose schedule than Blissel®.

**Figure1.** Study Design

[figure not shown]

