## SUMMARY OF THE STUDY PROTOCOL

**Study Title:** A PHASE II PROSPECTIVE, RANDOMIZED, DOUBLE-BLIND, PLACEBO-CONTROLLED AND MULTI-CENTRE CLINICAL TRIAL TO ASSESS THE SAFETY OF 0.005% ESTRIOL VAGINAL GEL IN HORMONE RECEPTOR-POSITIVE POSTMENOPAUSAL WOMEN WITH EARLY STAGE BREAST CANCER IN TREATMENT WITH AROMATASE INHIBITOR IN THE ADJUVANT SETTING. “BLISSAFE Study”

**Sponsor Study Code:** ITFE-2026-C10

**Sponsor:** ITF RESEARCH PHARMA S.L.U

**Countries and number of sites:** Spain and Sweden. 5 participating sites approximately

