## **5.3 Method of Assigning a Patient to a Treatment**

All patients will be screened prior to entry on this study. An explanation of the study and discussion of the expected side effects and presentation of the informed consent document will take place. Eligible and consenting patients will be enrolled into the study and a screening code will be assigned to the patients.

All patients who meet all inclusion and exclusion criteria will be randomized to receive 0.005% estriol vaginal gel (Blissel®) or placebo vaginal gel.

A randomization list will be generated taking into consideration blocks of 5 (4 actives 1 placebo). The study medication will be coded according to this randomization list. Study medications will be shipped in blocks of 5 to the sites.

In each site, all patients that fulfil all inclusion and exclusion criteria and are definitely included in the study will be assigned the randomization code. This code will be the one labelled in the medications. Thus, the first patient included in a site will receive the first study medication in the block, the second patient included will receive the second medication in the block, and this procedure will be followed consecutively.

The eligibility checklist must be completed and signed by the investigator prior to inclusion and it must be included into medical history of each patient.

All eligible patients enrolled in the study will be entered in a patient registration log maintained by the Site and in the Trial Master File.

The study treatment must be administered after definite inclusion of the patient in the study.

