#### **8.2.7.2 Vaginal Maturation value and pH**

The averages of the differences between the baseline and the final MV and pH of the 0.005% Estriol vaginal gel and placebo groups will be shared by a non-parametric test., to determine the possible superiority of the 0.005% Estriol vaginal gel treatment compared with placebo administration.

These same tests will be used to analyse the change in the MV and pH after the initial observation period of 3 weeks.

All of the above secondary analyses will be conducted at a two-sided 0.05 level of significance.

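### Randomisation is stratified by site, but the named tests for hormones, signs and symptoms carry no site term, so they are conservative and lose some power to the extent that site matters

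*Protocol*

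**What the plan says.** Section 3.1 makes site the only stratification factor: "Sixty patients will be randomized (stratified by site) to receive 0.005% estriol vaginal gel (arm A". The split is fixed as "in a 4:1 proportion, so 48 patients will enter in arm A and 12 in arm B". Section 5.3 puts this into practice: "A randomization list will be generated taking into consideration blocks of 5 (4 actives 1 placebo". Medication is shipped to sites in those blocks and used in order. The Summary gives "5 participating sites approximately", in Spain and Sweden.

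The analysis sections do not take site up again:

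- **Primary FSH (8.2.7):** the change from baseline to week 12 "and comparing by arm will be analyzed using a non-parametric test (Mann-Whitney-Wilcoxon test").
- **Supporting ANCOVA (8.2.7):** "The ANCOVA analysis will compare the variation of FSH 12 weeks adjusted by FSH basal between the two arms". Baseline FSH is the only covariate.
- **Signs and symptoms (8.2.7):** Mann-Whitney-Wilcoxon, no site term.
- **All hormones (8.2.6):** Mann-Whitney-Wilcoxon, or ANCOVA adjusted for the initial value, no site term.
- **Maturation value and pH (8.2.7.2):** an unspecified non-parametric test, then for week 3: "These same tests will be used to analyse the change in the MV and pH after the initial observation period of 3 weeks".

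On level, section 8.2.3 states: "The significance level of all statistical tests is established at 0.05". Section 8.2.1 leaves detailed methods to a SAP, but requires a protocol amendment for a major change to the primary analysis.

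**The concern.** Allocating 4:1 within each site balances the arms on site. Differences between sites then largely cancel from the arm comparison, so its real sampling error contains little between-site variation. A test that ignores site still counts that variation as noise. Its standard error is too large, its true type I error falls below 5%, and it rejects less often than a test that uses the design.

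Two features make this worth raising. The placebo arm has only 12 women, so avoidable noise is costly. And the study hypothesis (section 1.6) is that there is no significant decline in gonadotropin. For FSH, a test that rejects too rarely errs towards the reading the study hopes for.

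**Working it through.** **1. The plan's own figures.** FSH effect 75.7 − 66.0 = 9.7 mIU/ml, SD 22.3 (section 8.1). A paired two-sided t-test with n = 44 has 80.5% power (79.6% at 43), so the stated 44 reproduces. For maturation value, effect 24.9 − 0.6 = 24.3, SD 24.2, 44 against 11: power is 83.3% by the t-test, above the stated 80%. Neither calculation involves site, and neither is wrong because of it.

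**2. Expected direction.** Let ρ be the share of variance in change from baseline that lies between sites. With balance within site, the true error variance is proportional to 1 − ρ. With site sizes 10, 10, 10, 15, 15, the unstratified test counts on average about (1 − ρ) + ρ × [1 − (3×10² + 2×15²)/60²] = 1 − ρ + 0.79ρ. The approximate true size is 2Φ(−1.96 / √[(1 − ρ)/(1 − 0.21ρ)]):

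- ρ = 10%: √(0.900/0.979) = 0.959; 1.96/0.959 = 2.04; size about 4.1%
- ρ = 20%: √(0.800/0.958) = 0.914; 1.96/0.914 = 2.14; size about 3.2%
- ρ = 30%: √(0.700/0.937) = 0.864; 1.96/0.864 = 2.27; size about 2.3%

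**3. Simulation.** Inputs from the protocol: 60 women, about 5 sites, blocks of 5 (4 active, 1 placebo), nominal 0.05. Assumed: the site sizes above, Normal change scores with total variance 1, random site effects, two-sided tests (the protocol does not state sidedness for the primary test), a non-prognostic baseline in the ANCOVA, no dropout, and ρ from 0 to 30%. There were 20,000 null runs and 8,000 power runs per setting.

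True size (%):

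| ρ | Mann-Whitney | van Elteren | ANCOVA, no site | ANCOVA + site |
|---|---|---|---|---|
| 0 | 4.8 | 4.9 | 5.0 | 5.0 |
| 5% | 4.3 | 5.0 | 4.6 | 5.1 |
| 10% | 3.8 | 4.8 | 4.0 | 4.9 |
| 20% | 3.3 | 4.8 | 3.5 | 5.1 |
| 30% | 2.6 | 4.7 | 2.7 | 5.1 |

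Power (%), columns in the same order. FSH is 9.7/22.3 = 0.43 SD; maturation value (MV) is 24.3/24.2 = 1.00 SD:

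| ρ | FSH | MV |
|---|---|---|
| 0 | 24 / 23 / 25 / 25 | 84 / 82 / 86 / 86 |
| 5% | 24 / 24 / 25 / 27 | 84 / 83 / 87 / 87 |
| 10% | 24 / 26 / 26 / 28 | 86 / 85 / 87 / 89 |
| 20% | 24 / 28 / 25 / 31 | 87 / 89 / 89 / 92 |
| 30% | 24 / 32 / 26 / 35 | 89 / 93 / 91 / 95 |

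**4. A rank test that uses site.** Van Elteren loses 1 to 3 points when site explains nothing. A site-aligned rank test (subtract the site mean, rank all women together, use the within-site permutation variance) does not. With the same sites, a shift of 0.95 SD chosen to give about 80% power, and 6,000 runs per setting:

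| ρ | Size: Mann-Whitney / aligned | Power: Mann-Whitney / aligned |
|---|---|---|
| 0 | 4.8 / 5.0 | 79.3 / 79.4 |
| 5% | 4.3 / 4.8 | 80.6 / 81.9 |
| 10% | 3.8 / 4.7 | 81.2 / 84.2 |
| 20% | 3.2 / 5.1 | 83.0 / 87.8 |
| 30% | 2.7 / 5.0 | 84.8 / 92.0 |

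At the FSH effect of 0.43 SD, Mann-Whitney against aligned rank gives 24 against 25% at ρ = 0, 25 against 26% at 5%, 23 against 26% at 10%, and 23 against 33% at 30%. Uneven sites (24/14/11/7/4) gave the same pattern at 0.95 SD.

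**The case against.** The strongest reply is that the loss is conditional and may be small where it matters most. FSH and LH are assayed at one central laboratory, the estrogens at another, and maturation smears are also read centrally (sections 6.1, 6.2, 6.4). Every endpoint is a change from baseline, which removes stable site differences. At ρ up to 5% the cost is about one power point. This stands, and it is why the size is given as a range that starts at nil. It has less force for signs scored by the investigator and pH strips colour-matched at the site.

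A second reply is that site terms and pooling rules are SAP matter. This stands in part. But section 8.2.7 itself fixes the primary test and the ANCOVA covariate, and section 8.2.1 limits how far a SAP can depart from them without an amendment.

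Third, the aligned rank test is uncommon, and these simulations used Normal data, so its behaviour on 0 to 3 scores with many ties is not shown here. That also stands.

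Stronger readings that a reader might infer are not supported:

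- **That the tests are invalid or the type I error is inflated.** The error runs only in the conservative direction.
- **That the sample size is wrong.** The 44 rests on a within-arm calculation, and unstratified power for a given total SD does not fall as ρ grows.
- **That an unstratified test is fixed for maturation value and pH.** Section 8.2.7.2 names no test, and a site-stratified one would fit its words.
- **That adjusting for site would make the FSH comparison informative.** It would not. Between-arm FSH power is about 24% at the protocol's own effect, which is a separate and larger issue.

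**Conclusion.** The mismatch between design and analysis is in the text: allocation is balanced within site, while the named tests for hormones, signs and symptoms and the supporting ANCOVA ignore site. The direction of the effect is certain, but its size is not, because the protocol gives no between-site share of variance in change from baseline.

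Over an assumed 0 to 30%, the true size of the 5% Mann-Whitney test runs from about 4.8% to 2.6%. The power given up is about 0 to 1 point at shares up to 5% and about 3 at 10% (nearer 2 for the maturation value ANCOVA). At 20 to 30% it is about 5 to 10 points, or 3 to 4 for the maturation value ANCOVA, where power is already near 90%. These figures rest on Normal outcomes, five sites and full data on 60 women. The change is worth making because it is cheap and costs no measurable power if site turns out not to matter.

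**What to change.** - In sections 8.2.6 and 8.2.7, add site as a factor in the ANCOVA.
- In the same sections, make the rank comparisons account for site, for example by a site-aligned rank test with within-site permutation variance. Van Elteren is the more familiar choice but can lose 1 to 3 points if site explains little. For the 0 to 3 scores, check the chosen test on tied data first.
- In section 8.2.7.2, name the test for maturation value and pH and say that it accounts for site.
- Before unblinding, fix a rule that pools small sites within country, based on site size and never on arm. With sites of 24/14/11/7/4, about 20% of simulated trials had a site without a placebo woman: a site of 4 uses four places of a block of 5 and misses its one placebo with probability 1/5.

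The cost is a few degrees of freedom, a less familiar rank test, some SAP text and code, and a protocol amendment if the change to the primary test counts as major under section 8.2.1. No new data are needed. If the sponsor prefers to keep the unstratified tests, the protocol should say why site is omitted.
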